## Abstract

**Background:** Antidepressants are commonly prescribed by primary care providers for treating depression, anxiety, and other conditions. A trial and error approach is typically used to identify effective therapy. Treatment efficacy and safety of many antidepressants can vary based on the presence of certain diseases and metabolism gene types. Pharmacogenomic (PGx) testing provides phenotypic classification of individuals as poor, intermediate, extensive, and ultra-rapid CYP450 metabolizers. This allows more accurate drug selection for efficacy and dosing to minimize toxicity.

**Objective:** To determine the preliminary effectiveness of PGx testing for selection of effective antidepressant, medication adherence, depressive symptoms, and healthcare utilization. To determine acceptability of PGx testing in primary care among patients and providers.

**Methods:** This is a 6-month randomized, wait-listed, controlled pilot trial conducted in 6 department of family medicine (DFM) clinics at the University of Michigan (UM). We will enroll physicians practicing at a UM DFM clinical site who are willing to utilize PGx test results in conjunction with treating patients prescribed certain antidepressants. We will also enroll patients of these DFM physicians who are adults with a new prescription for an antidepressant (within the past 4 weeks) including patients who have switched to a new antidepressant from another antidepressant or have added on a new antidepressant to current antidepressant therapy. Patients are excluded if taking an antidepressant for more than 4 weeks and if they have had PGx testing in the past.

Physician participants will complete a baseline survey to assess demographics, and knowledge, acceptability and utility of PGx testing for this population. At the conclusion of the study, physician participants will complete a semi-structured interview to assess knowledge, satisfaction, feasibility, acceptability, effectiveness, barriers to widespread adoption, and utility of PGx testing.

All patients will complete a baseline, 3-, and 6-month assessment; control patients will have an additional 9-month assessment. Data to be collected include reasons for antidepressant use, depression and anxiety symptoms and severity, functional health status (SF-12), PGx knowledge, work status changes, demographic information, physician and emergency department visits, adverse effects, and medication alterations and adherence.

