## 3.0 Objectives

PGx testing could greatly improve the use of antidepressants by aiding prescribers in identifying proper medications for individual patients; thus potentially improving medication adherence, as well as reducing symptoms and antidepressant side effects.

This pilot study will explore the use of PGx testing in primary care, and is guided by several specific aims:

Specific Aim 1: To determine the effect of PGx testing on the primary outcome of physician treatment decisions, as measured by the change in the proportion of patients who are prescribed medications at baseline that are contraindicated according to the PGx test, compared to the proportion at six-month follow-up.

Specific Aim 2: To determine the effect of PGx testing on secondary outcomes measures of interest, including change in symptoms and severity and medication adherence from baseline to six-month follow-up.

Specific Aim 3: To determine the acceptability of PGx testing in primary care among patients and physicians.

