**Table 1: Physician Participant Measures**

Construct	Measure	Assessment Time	
		Baseline	Post-Study
Demographic information and characteristics of physicians	Investigator Developed Semi-Structured Interview and Survey	X	
Knowledge of PGx testing		X	X
Acceptability of PGx testing		X	X
Utility of PGx testing		X	X
Effectiveness of PGx testing		X	X
Feasibility of PGx testing		X	X
Barriers to PGx testing		X	X
Satisfaction with PGx testing		X	X

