### **5.5.2 Patient Participants**

Patient participants will be screened for inclusion/exclusion criteria prior to consent and enrollment. After enrollment, all patient participants will complete a baseline, 3-, and 6-month assessment. Control patients will have an additional 9-month assessment of the previously mentioned items. All baseline data will be collected via paper forms and then transferred into REDCap, whereas 3-, 6-, and 9-month assessments will be conducted via phone and entered directly into REDCap by study personnel. The constructs, measures, and data collection times are shown in Table 2. In addition to these measures collected during data collection visits, data will be extracted from MiChart to document treatment, including medication changes, and healthcare utilization for patient participants during the study. We will also extract any available PHQ-9 and GAD-7 data, which is now collected as a part of routine clinical practice. Surveys/interviews will be audio recorded when permitted by participants.

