**Table 2. Patient Participant Measures**

Construct	Measure	Assessment Time			
		Baseline (via paper survey)	3 months (via phone)	6 months (via phone)	9 months (Control Only; via phone)
Reason antidepressant was prescribed		X	X	X	X
Depression Symptoms and Severity	Personal Health Questionnaire Depression Scale (PHQ-8)	X	X	X	X
Anxiety Symptoms and Severity	Generalized Anxiety Disorder 7-Item Scale (GAD-7)	X	X	X	X
Functional Health Status	12-Item Short Form Survey (SF-12)	X	X	X	X
PGx Knowledge	Investigator Developed	X			X
Missed days of work	Work Productivity and Activity Impairment Questionnaire (WPAI)	X	X	X	X
Demographic information		X			
Health history	Smoking history, BMI	X			
Healthcare utilization	Physician visits, hospital and ER admissions	X	X	X	X
Adverse Drug Reactions	Antidepressant Side- Effect Checklist (ASEC)	X	X	X	X
Medication and medication changes	Medications prescribed and number of medication changes	X	X	X	X
Medication Adherence	Adherence to Refills and Medication Scale (ARMS)	X	X	X	X
	Pill count	X	X	X	X
	Three-Item Self-rated Adherence Scale	X	X	X	X

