## 5.6 Data Analyses

In this study, we expect to enroll up to 30 physician participants and expect a retention rate of 90-100%. We also expect to enroll about 100 patient participants and expect a retention rate of 80% at the completion of this study.

Data from this study will be analyzed by the study statistician. Survey data will be analyzed using descriptive statistics. Multiple-choice questions will be analyzed using standard quantitative techniques including Chi square and t-test. Open-ended responses will be independently coded using qualitative methods, including any transcripts that result from the recorded survey responses.

Independent sample t-tests will be used to compare outcomes between intervention and control groups at each time point, as well as at similar time points after test results were released to physicians (i.e. baseline for intervention vs. 3 month for control group). Linear mixed models will assess the change in outcomes, as well as whether the change is similar between groups. This will be done by including time, study group, and a time by study group interaction as predictors of each outcome. Time will be considered in two ways, first as the time in study, and secondly as time since test results were released to physicians. In the latter, only data from 3-month to 9-month will be included for the control group, and baseline to 6-month for intervention group, due to timing of test result release. Models will be adjusted for patient demographics.

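### Aim 3 promises acceptability among patients, but the text shown names no patient acceptability measure; separately, patient PGx knowledge has no follow-up value in the intervention arm

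*Combined protocol and SAP*

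**What the plan says.** Section 3.0 states Specific Aim 3 as "To determine the acceptability of PGx testing in primary care among patients and physicians". The abstract's objective matches it: "To determine acceptability of PGx testing in primary care among patients and providers".

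For physicians, section 5.5.1 describes the content of the surveys and closing interview. Table 1 has a row "Acceptability of PGx testing" and a separate row for satisfaction, both marked at baseline and post-study.

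For patients, section 5.5.2 defers to a table: "The constructs, measures, and data collection times are shown in Table 2". It adds chart extraction of treatment, medication changes, healthcare use and any routine PHQ-9 and GAD-7 scores, and it allows audio recording of surveys and interviews. The abstract's patient list begins "Data to be collected include reasons for antidepressant use, depression and anxiety symptoms and severity, functional health status (SF-12), PGx knowledge, work status changes" and goes on to demographics, visits, adverse effects and medication use.

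Table 2 marks patient PGx knowledge at baseline and in one later column, headed "9 months (Control Only; via phone". Section 5.1 follows intervention patients for 6 months and controls for 9, with controls' results released to physicians at three months. For analysis, section 5.6 states: "Independent sample t-tests will be used to compare outcomes between intervention and control groups at each time point". It also plans mixed models with time, group and their interaction, on time in study and on time since release. It says survey data will be described and open-ended responses coded.

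**The concern.** Acceptability is one of three specific aims of this pilot, and patients are one of the two groups in which it is to be determined. An aim with no named measure, assessment time or summary for one of its groups cannot be reported for that group from the plan as written. Opinions not asked for on the scheduled calls cannot be recovered later.

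The knowledge schedule raises a lesser issue. Knowledge is the only patient construct followed up in one arm alone. A rise in controls between baseline and month 9 would have no counterpart in the intervention arm to be read against.

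**Working it through.** The plan states no figure on this point, so there is none to reproduce. The check sets the passages side by side and then counts what Table 2 allows.

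**Acceptability**

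| Place | Patients | Physicians |
|---|---|---|
| Abstract objective, Aim 3 | promised | promised |
| Measures table | Table 2: 0 of 12 constructs | Table 1: 2 of 8 (acceptability, satisfaction) |
| Section 5.5 text | 5.5.2: not named | 5.5.1: named |
| Abstract, Methods | not in the patient list | named |
| Section 5.6 | general methods, no item named | general methods, no item named |

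**Knowledge**

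1. Table 2 has 12 constructs: 9 at all four assessments, 2 at baseline only, and PGx knowledge at baseline and month 9 (9 + 2 + 1 = 12).
2. The payments in section 5.2.2 confirm that intervention patients have no month 9 call: 3 × $20 = $60 for intervention, 4 × $20 = $80 for control.
3. With equal randomisation, 100 / 2 = 50 per arm. Applying the stated 80% retention to each arm (an assumption), 50 × 0.80 = 40 controls have a follow-up knowledge value. The intervention arm has 0.
4. Between-arm t-tests possible for knowledge: at study months 0, 3 and 6, only month 0 (1 of 3). At 0, 3 and 6 months since release, none (0 of 3).
5. The section 5.6 model has four coefficients: intercept, time, group, group × time. Code control as 0 and intervention as 1.
   - Time in study: intervention at 0 gives (1, 0, 1, 0); control at 0 and 9 gives (1, 0, 0, 0) and (1, 9, 0, 0). The rank is 3 of 4 and the interaction column is all zeros.
   - Time since release: intervention at 0 gives (1, 0, 1, 0); control at 9 − 3 = 6 gives (1, 6, 0, 0). The rank is 2 of 4.
   - The interaction cannot be estimated on either scale.
6. With month 6 added in both arms, time in study has intervention 0, 6 and control 0, 6, 9. Time since release has intervention 0, 6 and control 6 − 3 = 3, 9 − 3 = 6. The rank is 4 of 4 on both. The possible t-tests become 2 of 3 (months 0 and 6) and 1 of 3 (six months since release).

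**How many calls may already be past**

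The first reference in section 10.0 was accessed on 4-10-18, so this text dates from April 2018 or later. Section 6.0 plans enrolment over six quarters, Q1 2017 to Q2 2018. A patient enrolled by 30 September 2017 reached month 6 by 30 March 2018. On the planned timeline, the 6-month calls for three of the six enrolment quarters were therefore already past. If enrolment were even (an assumption), that is 3/6 × 100 = 50 patients.

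**The case against.** **Acceptability may be covered in material not shown.** Patient interviews may be recorded, open-ended answers are to be coded, the abstract's list is not exhaustive, and neither Figure 2 nor the survey forms can be seen. This stands as a limit. A reader might infer that patients will never be asked about acceptability, and the documents do not support that. They support only that no such measure is named, scheduled or given a summary in the text shown. Section 5.6 already has general methods that could handle the items once they exist.

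**Enrolment might serve as evidence of acceptability.** It cannot among participants, because section 5.4.2 makes willingness to be tested an entry criterion. Nor can knowledge stand in: Table 1 treats knowledge and acceptability as separate constructs.

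**Knowledge may never have been meant for the between-arm models.** This is a fair point. Section 5.6 applies the t-tests and models to outcomes and gives survey data descriptive statistics, and knowledge is in no named aim. The rank calculation adds little to the plain statement that one arm has no follow-up value. It matters only if knowledge is treated as an outcome, which the plan leaves open.

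**A reader might infer that other passages contradict Table 2 on knowledge.** They do not. The abstract's list is not a schedule; it also contains demographics, which Table 2 marks at baseline only. Section 5.5.2 says "Control patients will have an additional 9-month assessment of the previously mentioned items", but that concerns the control call at which Table 2 does mark knowledge. Neither passage places knowledge at month 3 or 6.

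**Conclusion.** The main point holds for the text shown: acceptability or satisfaction appears in 0 of 12 patient constructs against 2 of 8 physician constructs, so the patient half of Aim 3 has no named measure. The physician half is covered, and the primary outcome under Aim 1 is unaffected. The change should be made, but the gap does not undermine the trial as a whole.

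The smaller point also holds. If Table 2 is followed, about 40 controls and no intervention patients have a follow-up knowledge value. Description, the baseline comparison and the control change from baseline to month 9 remain possible. A between-arm comparison after baseline, a comparison at matched time since release, and the interaction do not. This reading depends on column positions in a table extracted from PDF. The knowledge row has the same number of fields as the demographic row, so a shifted column is unlikely.

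**What to change.** 1. Add a short patient acceptability block to Table 2 at the 6-month call in both arms, and repeat it at month 9 for controls. The repeat gives both arms a value six months after release, since at month 6 controls are only three months past it. Preferably record whether the physician had shared the result, because section 5.1 leaves that to the physician and some patients may be judging a test whose result they never heard.
2. State in section 5.6 that the block is summarised descriptively by arm.
3. For knowledge, either add the items at the 6-month call in both arms and keep month 9 for controls, or state that knowledge is descriptive and excluded from the between-arm analyses. If month 6 is added, the report should say that this comparison sets six months since release against three, because both arms' results are out by then.

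The cost is a few minutes on calls not yet made, plus edits to Table 2 and section 5.6; no new visits or calls are needed. Given the date of this text, patients already past the call would lack the new items. The report should therefore give the number asked, by arm, alongside the number enrolled.

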## 4.0 Resources and Personnel

### 4.1 Setting

This study will be conducted with physicians and patients recruited from the University of Michigan (UM) Department of Family Medicine (DFM), which has six clinical sites; Briarwood (Ann Arbor), Domino's Farms (Ann Arbor), Ypsilanti, Chelsea, Dexter, and Livonia.

## 4.3 External Partners

All blood specimens will be sent for analysis to Progenity, a CLIA-accredited molecular diagnostics laboratory in Ann Arbor, MI. Progenity will provide a report for each sample to the study staff via MiShare or other secure transmission method, who will in turn release the results to physicians, along with any treatment recommendations based on the test results, via MiChart. The arrangement between UM and Progenity is covered by a contract.

## 5.0 Study Procedures

### 5.1 Study Design

This study will include two different populations of participants; primary care physicians and their patients who have been recently prescribed and taking one of the following antidepressants: citalopram (Celexa), escitalopram (Lexapro), fluoxetine (Prozac, Prozac Weekly, Rapiflux, Sarafem, Selfemra), fluvoxamine (Luvox, Luvox CR), paroxetine (Paxil, Paxil CR), sertraline (Zoloft), duloxetine (Cymbalta, Irenka), venlafaxine (Effexor, Effexor XR), nortriptyline (Aventyl, Pamelor), bupropion (Forfivo, XL, Wellbutrin, Wellbutrin SR, Wellbutrin XL), mirtazapine (Remeron, Remeron Soltab), or vortioxetine (Trintellix). We will recruit and enroll approximately 30 UM DFM physicians to participate in this study. For physician participants, we will obtain consent and then conduct assessments of baseline PGx knowledge, as well as semi-structured interviews and surveys regarding their experiences at the conclusion of the study. Please see Figure 1 for physician participant study flow.

From those participating physicians, we will recruit 100 of their adult patients who have been newly prescribed one of the antidepressants listed above. These patient participants will be enrolled in a six-month randomized wait-listed control pilot study.

Patient participants will meet with study staff for consent and baseline data collection at a Michigan Clinical Research Unit (MCRU) in either Domino's Farms or the Cardiovascular Center. Once consent and baseline data collection are complete, participants will have their blood drawn by MCRU laboratory staff. A single 4 mL Lavender top EDTA tube of blood will be drawn. Once the blood draw is complete, study staff will send the sample to Progenity for analysis. After the baseline assessment is complete, patient participants will be randomized equally to either have their test results sent immediately to their participating primary care physicians once available, or to have their test results sent in three months. Randomization will be stratified by physician in ten block units to ensure balance by physician. PharmDs on the research team ([name] and [name]) will be available to consult with physician participants at any time during the study; however, our study PharmDs will meet with each participating physician at least once, when their first patient PGx test results are available to provide general, as well as patient specific education about the PGx test and results. These consultations will help physicians to interpret PGx test results, and may help to guide treatment decisions, if necessary. Study pharmacists or staff will not

provide PGx results to patients; it is up to the patient's physician to provide this information if he/she feels it is appropriate. Likewise, although study pharmacists may make treatment recommendations based on the PGx test results, it is up to the treating physician to decide whether to act on those recommendations. All intervention patient participants will be followed for a total of 6 months, with phone-based follow-up assessments occurring at 3- and 6-months. All control patients will be followed for 9 months, with phone-based follow-up assessments occurring at 3-, 6-, and 9-months. Please see Figure 2 for patient participant study flow.

Figure 1. Physician Participant Study Flow

[figure not shown]
[figure not shown]

Figure 2: Patient Participant Study Flow

Physicians and patients enrolled in this study will be exposed to minimal risk. Participants in both arms of the study will undergo PGx testing. Physicians for intervention group participants will receive PGx test results as soon as they are available, whereas those participants in the waitlisted control group will receive their test results three months after enrollment. Because the current standard of care does not involve the use of PGx testing, our waitlisted control group is not exposed to any additional risk above and beyond usual care. To clarify, the intervention under investigation in this study is the PGx test. We will not directly intervene in the clinical care of a patient, as all clinical decision making is at the discretion of the physician managing a patient's care. All participants in this study may benefit because their antidepressant medication may be tailored to their pharmacogenomic profile. Although both populations of participants run risks associated with breaches of privacy due to electronic storage of study data, every effort will be made to minimize these risks.

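### Physician is the randomisation stratum and makes the decision that is the primary outcome, yet no planned analysis names physician; this matters mainly for standard errors of baseline to six-month change

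*Combined protocol and SAP*

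**What the plan says.** Section 5.1 (Study Design) sets the size and the allocation: "We will recruit and enroll approximately 30 UM DFM physicians to participate in this study", and from those physicians "we will recruit 100 of their adult patients". Patients are allocated equally to the two arms, and "Randomization will be stratified by physician in ten block units to ensure balance by physician". Physician is the only stratification factor named.

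Section 3.0 (Objectives) names "the primary outcome of physician treatment decisions" as the target of Aim 1. This outcome is defined "as measured by the change in the proportion of patients who are prescribed medications at baseline that are contraindicated according to the PGx test", with the six-month proportion as the comparator.

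Section 5.6 (Data Analyses) plans chi-square tests and t-tests for survey items. For outcomes, "Independent sample t-tests will be used to compare outcomes between intervention and control groups at each time point". It adds that "Linear mixed models will assess the change in outcomes, as well as whether the change is similar between groups", and explains: "This will be done by including time, study group, and a time by study group interaction as predictors of each outcome". The models are also adjusted for patient demographics. In this section physicians appear only as a number to be enrolled and retained, and as the recipients of test results, which fixes a time origin. Physician is never a covariate, stratum, random effect or cluster. The mixed models list their fixed effects but no random effects of any kind.

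**The concern.** When allocation is stratified, the analysis would normally account for the stratum. Here the stratum is also the person whose decision is measured. Section 5.1 has the study pharmacists meet each physician when that physician's first results arrive, and leaves it to the physician whether to act on recommendations. Patients of one physician may therefore change medication in similar ways.

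Two quantities are affected, in different directions. The comparison between arms is made largely within physicians, so ignoring physician leaves variation in the error term that could have been removed. The cost is a little precision. Change from baseline in one arm, or averaged over arms, gains nothing from that within-physician contrast. If change clusters by physician, a standard error that treats patients as independent is too small, and a change could look better established than it is. Aim 1 is worded as such a change, and section 5.6 says the models will assess change.

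**Working it through.** The plan gives no ICC, significance level or power figure, so there is no figure of its own to reproduce. ICCs of 0.01, 0.05, 0.10 and 0.20 and a nominal 5% two-sided test are assumed throughout.

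**Inputs from the plan.** About 30 physicians and 100 patients (5.1), so 100/30 = 3.33 patients per physician; equal allocation; 80% patient retention (5.6). The allocation sentence is read as permuted blocks of ten within physician. Equal recruitment means 20 physicians with 3 patients and 10 with 4.

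**1. Balance within physician.** A block of ten forces a 5:5 split only at the tenth patient.
- P(3 patients all in one arm) = 2·C(5,3)/C(10,3) = 20/120 = 16.7%.
- P(4 patients all in one arm) = 2·C(5,4)/C(10,4) = 10/210 = 4.8%.
- Expected physicians with patients in one arm only: 20 × 0.167 + 10 × 0.048 = 3.8 of 30.
- Under simple randomisation: 20 × 0.25 + 10 × 0.125 = 6.25.

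Balance is approximate, but better than without blocks.

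**2. Comparison between arms.** Over simulated allocations, the expected standard error without physician was compared with that from a random-intercept model.

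| ICC | 0.01 | 0.05 | 0.10 | 0.20 |
|---|---|---|---|---|
| SE larger by | 0.1% | 0.9% | 2.2% | 6.0% |
| t-test type I error | 4.9% | 4.6% | 4.8% | 4.3% |

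**3. Change from baseline, equal recruitment.** The variance of a mean change is multiplied by DE = 1 + (q − 1)·ICC, where q is the sum of squared patient counts per physician divided by the number of patients. Type I error of a test that ignores this is about 2·[1 − Φ(1.96/√DE)].

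- One arm. The number of a physician's patients in one arm has mean 1.5 and variance 3 × 0.25 × 7/9 = 0.583 for 3 patients, and mean 2 and variance 4 × 0.25 × 6/9 = 0.667 for 4. So q ≈ [20 × (2.25 + 0.583) + 10 × (4 + 0.667)]/50 = 103.3/50 = 2.07. At ICC 0.20, DE = 1 + 1.07 × 0.20 = 1.21 and type I error is about 7.5%.
- Averaged over arms. q = (20 × 9 + 10 × 16)/100 = 3.4. At ICC 0.20, DE = 1 + 2.4 × 0.20 = 1.48 and type I error is about 10.7%.

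Simulation (20,000 trials per cell, normal change score, one-sample t-test ignoring physician) agrees with these formulas and extends them to uneven recruitment, modelled as a flat Dirichlet over 30 physicians:

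| Type I error at ICC | 0.01 | 0.05 | 0.10 | 0.20 |
|---|---|---|---|---|
| One arm, equal | 5.1% | 5.4% | 6.1% | 7.5% |
| One arm, very uneven | 5.5% | 6.8% | 8.3% | 11.7% |
| Averaged, equal | 5.2% | 6.3% | 7.7% | 11.0% |
| Averaged, very uneven | 5.5% | 9.1% | 12.1% | 19.3% |

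With 20 patients dropped at random the one-arm equal row becomes 4.9, 5.6, 6.0 and 7.1%.

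**4. Which remedy acts on change.** A physician intercept is constant over time and cancels from within-patient contrasts. With complete data at two time points, the generalised least squares standard errors for time and for time by group were identical with and without it (0.1348 and 0.2010). Clustered standard errors do act on change. In the simulated cells of step 3, with full and with 80% retention, ordinary clustered standard errors gave 4.9 to 5.5% with equal recruitment but 5.8 to 6.9% with uneven recruitment. With a small-sample correction (CR2, Satterthwaite degrees of freedom) they gave 4.7 to 5.6% throughout.

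**The case against.** The strongest reply is that little depends on this. Blocks of ten improve balance, chance imbalance biases nothing, and the t-test between arms keeps its level. All of that stands. A reader might infer that unfilled blocks distort the arm comparison, or that the t-tests are invalid; the figures in step 2 support neither.

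Second, the mixed models do not exclude physician; they are silent. A reader might infer that the plan leaves physician out of them, but the text supports only that their random effects are unstated. That is still a gap, because the models cannot be reproduced as written.

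Third, the harm is conditional. It needs physician to be ignored in fact and an ICC for change well above 0.01. Clustering may be low, since whether a drug is contraindicated depends partly on the patient's own genotype. The largest entries (11.0% and 19.3%) belong to a test averaged over arms. Section 5.6 specifies no such test, and with the interaction in the model and usual coding the time effect is specific to an arm. A reader might quote 19.3% as the trial's error rate. The documents do not support that: it also needs an ICC of 0.20 and very uneven recruitment, and they give neither.

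Finally, Aim 1 is a paired binary outcome, so figures from normal data are approximate for it. This limits their precision but does not change their direction.

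**Conclusion.** The concern holds in a limited form. Section 5.6 uses the randomisation stratum in no analysis, although the primary outcome is that stratum's own decision. Between arms the consequence is a small loss of precision. For baseline to six-month change, the type I error of a nominal 5% test within one arm is about 5 to 8% with equal recruitment. It reaches 11.7% with very uneven recruitment at the highest ICC considered, and is higher still only if arms are averaged.

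These sizes rest on assumed ICCs, on the block-of-ten reading of a loosely worded sentence, and on normal change scores. The gap in the plan does not depend on them. For a pilot this is an improvement worth making, not a flaw that undermines the trial.

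**What to change.** In section 5.6:

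1. State the random effects of the mixed models, including the patient-level effect.
2. For comparisons between arms at each time point, include physician as a random intercept. The t-tests may stay as simple unadjusted comparisons.
3. For change over time, including Aim 1, and for the time-by-group effect, add a physician-by-time random effect, or use physician-clustered standard errors with a small-sample correction such as CR2 with Satterthwaite degrees of freedom. A physician intercept alone is not enough here, as step 4 shows.

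As a minor clarification only, section 5.1 could say that blocks of ten at about 3.3 patients per physician give approximate balance. This alters no result, and no change to allocation is requested.

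The cost is a few lines of text, a little more analysis work and no new data. Using about 29 instead of 99 degrees of freedom widens the interval for an averaged change by 2.045/1.984 − 1, about 3%, even with no clustering, and by more if recruitment is uneven.
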